A Comparison of Treatment Methods for Patients Following
Total Knee Replacement

University of Pittsburgh

PCORI Award Number: CER – 1310-06994

Study Principal Investigator: [name]

Trial Registration: ClinicalTrials.gov Identifier NCT02237911

08/31/2014

A Comparison of Treatment Methods for Patients Following Total Knee Replacement.

Study Protocol

Design Overview - This comparative effectiveness study is designed to combine patient-centered research questions with rigorous research methods that minimize bias and balance internal and external validity. The pragmatic randomized clinical trial was selected to compare the treatments in ways in which they are delivered in routine clinical practice, so improving generalizability when informing what interventions work best. This will be a three group, single blind, pragmatic randomized clinical trial to answer the question: “In patients at later stages post TKR, given their personal characteristics, what are the comparative effectiveness and harms of the interventions available to them, among individual outpatient rehabilitative exercise, community-based group exercise classes, and usual medical care, especially with regard to physical function and activity?” This study focuses on: (1) outcomes of physical function and activity, both genuinely important to patients, (2) identifying predictors of functional recovery, and (3) potential harms of comparators. The design is depicted in the Figure above. In short, patients post-TKR will be informed about the study by their health care provider or by public announcement. Screening for eligibility will be done in two phases; over the telephone using a questionnaire, and in-person history and physical exam. Following pre-intervention evaluation, subjects will be randomized to one of the 3 groups:

1) clinic-based individual outpatient rehabilitative exercise; 2) community-based group exercise classes; or 3) usual medical care. The usual medical care group will continue their usual care whereas the other two groups will exercise during 12 weeks.

Endpoint measures will be assessed prior to and after intervention (3 months), and 6 months after randomization. After the 6 months follow-up, subjects in the usual medical care group will be randomized to either clinic-based individual outpatient rehabilitation exercise or community-based group exercise.

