majority of patients are discharged from physical therapy within 2 months post TKR.^{1-4,86,87} Hence, as this study will recruit patients who are at least two months post TKR, these patients will likely no longer be participating in any structured exercise program at the time of study enrollment. To avoid a potential confounder effect, we will exclude patients that are currently participating in structured exercises at the time of study enrollment. Our preliminary studies demonstrated that this exclusion criterion will only minimally affect recruitment. If patients in this group decide by themselves to participate in exercise AFTER they are enrolled into the study, information about frequency, duration, and content of exercises will be recorded and analyzed for their potential effect on the outcomes.

Volunteers assigned to the usual medical care arm will be randomized to an exercise arm after completing the 6-month control period. This will be done based on the request from the patients who helped to design this study. The patients said that they would be less likely to participate in the trial if they would not receive some clear benefit from it. Being able to receive exercise upon completion of the 6-month control period was considered by the patients a good alternative to equalize the potential benefits from study participation. Thus, we made the usual care group an effective wait list control group. This approach is further justified for the following reasons: 1) it is expected to enhance compliance in this group; 2) it addresses the ethical concern of asking volunteers to join an exercise research study and then asking them not to exercise; and 3) data from this group can be included in the analysis of Aim 2 and the exercise data can be included in the analysis of attrition. We believe one of the strengths of the proposed study is the attempt to compare the 3 interventions in the manner they occur in the clinical settings to accurately guide decision-making. After careful consideration of the comparison groups, we also decided against a control group in which we would match the level of attention (hour-per-hour) between the 3 intervention groups because that would deviate from our pragmatic approach to evaluate the interventions as they occur in the real world.

ANALYTIC METHODS

Sample Size

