Calculations of sample size were based on the primary endpoint of WOMAC-PF at 3 months. We propose to recruit a total of 240 subjects (96 in each exercise arm and 48 in the usual care group) to allow approximately 86 subjects in each exercise arm and 43 in the usual care group available for a complete case analysis at 3 months (assuming 10% attrition at 3 months). We propose a larger number of subjects in both exercises groups (outpatient rehabilitative exercise and community-based group exercise) because we expect a moderate effect size between these two interventions; whereas we propose a smaller number of subjects in the usual care group because we expect a large effect size between the usual medical care group and either of the exercise groups. Thus, with an alpha level of 0.05, 2 tails test, a sample size of 172 (n=86 in each exercise group) will provide 81% power to detect a difference as small as 3.3-point difference between the two exercise groups in WOMAC-PF (SD of 7.7 from our pilot work).¹¹ This would correspond to a difference in less than 2 activities (out of the 17 queried in the WOMAC-PF) having improved from “about moderate difficulty” to “no difficulty”. The sample size of 43 in the usual medical care group will provide 80% power to detect a difference of 5.2-point difference in WOMAC-PF between the usual medical care group and any exercise group. Power analysis was conducted in NCSS/PASS. Moreover, this sample size will provide adequate power (above 80%) to test the hypothesis related to the secondary outcomes (performance-based physical function and physical activity). For example, we will be able to detect differences between the two exercise groups as small as 0.7 sec in the stair climbing test, 0.4 in the chair-rise test, 0.02 m/sec in walking speed, 1.4 sec in the single leg stance, and 35 min/day in light intensity physical activity (based on SD of our own preliminary data). The differences we will be able to detect between the usual care and any intervention groups are as small as 1.01 sec in the stair climbing test, 0.54 in the chair-rise test, 0.03 m/sec in walking speed, 1.6 sec in the

PRINCIPAL INVESTIGATOR (LAST, FIRST, MIDDLE): [name]

single leg stance, and 49 min/day in light intensity physical activity. These differences are smaller than the known minimal detectable changes for these outcomes.⁸⁸⁻⁹⁰

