For Aim 2, we plan to assess predictors of response based on a minimum change score of 20% in BOTH the WOMAC-PF and the composite score of functional performance at 3 months, thus yielding a binary outcome. For this aim, we will have a combination of those initially randomized to one of the exercise arms and those in the usual care group who were later randomized to the exercise arms for a total of approximately 200. If the expected response rate ranges between 50% and 60%, we would be able to detect an odds ratio of 2.2 to 2.4 with 80% power assuming a binary predictor with 50% split in the sample. In addition, with approximately 100 responders, we will be able to accommodate 9 predictors in the multiple logistic regression based on rule of thumb guidelines for sample size in logistic regression (min of response/nonresponse/ (#predictors+1) \geq 10).

Data Analysis

[name] will oversee data analyses. We will evaluate the statistical properties of baseline and follow-up outcome measures, including potential outliers, normality and missing data. Measures of central tendency (means, medians, other percentiles) and dispersion (standard deviations, ranges) will be computed for continuous variables, whereas frequency distributions will be calculated for categorical data. Distributions of baseline characteristics will be compared between groups to assess effectiveness of randomization, and statistical or clinical differences will be adjusted in the analyses. Data transformations may be applied if needed and guided by clinical meaningfulness.

Hypothesis 1.1 - Subjects in Groups 1 and 2 will demonstrate better physical function as compared to Group 3.

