During our pilot study 100% of the patients completed the 2 month follow-up assessment;¹¹ however we are realistic and recognize that such retention rate is very optimistic for this study. Thus, in this study we estimate the attrition to be 10% at the 3 months follow-up. We also estimate the attrition to be 15% at 6 months, based on our pilot work and other studies with similar populations and timeframes. We will compare baseline characteristics between patients with and without the assessment at 3 and 6 months to assess potential biases in the complete case analysis. We will also try to obtain reasons for study drop out to assess the missing data mechanism (missing completely at random, missing at random, non-ignorable missingness). We will use several missing data methods for imputing data and re-analyze using intention to treat (as randomized) to assess the impact of missing data on our conclusions as recommended.⁹⁷ We

PRINCIPAL INVESTIGATOR (LAST, FIRST, MIDDLE): [name]

will first use multiple imputation (with M=10 imputations) which assumes the data are missing at random. Since the data could be missing not at random, we will use another approach of assigning the lowest observed scores for missing values differentially by treatment group (non-ignorable missingness). The approach assumes the missingness is directly related to the value of the missing data, i.e., the people who are missing data on function have worse function scores (did not come in for assessment because function was worse). Results of all approaches to missing data will be presented in the primary paper for our study. If our significance and interpretation of our treatment effect vary depending on the method of imputation, we will view any conclusions cautiously.

PATIENT POPULATION

Detailed reasoning of inclusion criteria is provided in Human Subjects.

Subjects will be included in the study if they underwent a unilateral TKR 2 to 4 months prior to study, are older than 60 years of age, experience functional limitation in daily activities (score in the WOMAC-PF of at least 9 points), *speak English sufficient to understand study instructions*, are willing to be randomized to one of the 3 treatment groups, and have medical clearance to participate in the study.

Subjects will be excluded if they:

- Have absolute or relative contraindications to exercise testing as established by the American College of Cardiology/American Heart Association;^{99,100}

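### Aim 2 pools usual-care patients who cross over to exercise 8 to 10 months after surgery, without defining their baseline, scheduling their outcome visit or marking them in the model

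*Combined protocol and SAP*

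**What the plan says.** The usual medical care part of the Interventions section makes this arm a wait-list control. After six months its patients are randomized to one of the two exercise programmes, and one stated justification is that "data from this group can be included in the analysis of Aim 2". The Sample Size section relies on this: the Aim 2 set combines the original exercise arms with "those in the usual care group who were later randomized to the exercise arms for a total of approximately 200".

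Under Hypothesis 2 in Data Analysis, a responder must change by at least 20% on both WOMAC-PF and the performance composite at 3 months. Baseline variables are screened one at a time at p<0.15 and then enter a multivariable logistic model. No term for cohort or time since surgery is named there, and time since surgery is not among the listed potential predictors.

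The Patient Population section sets entry at 2 to 4 months after surgery with a "score in the WOMAC-PF of at least 9 points". On visits, the Design Overview says "Endpoint measures will be assessed prior to and after intervention (3 months), and 6 months after randomization". Table 1 likewise has columns only for baseline, months 3 and 6, and the two telephone calls.

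**The concern.** Three things that Aim 2 needs for crossover patients are not fixed: which visit is baseline, which visit supplies the outcome, and how the model separates them from patients who began exercise six months earlier in their recovery. An analyst would have to settle all three after the data are in.

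Aim 2 asks whether function, impairments and psychosocial status at the start of exercise predict response. Each of these may differ systematically between 2 to 4 and 8 to 10 months after surgery, and so may the scope for further improvement. An unmarked cohort can therefore create an association with response or hide one. The p<0.15 screen is also exposed, since it works on unadjusted odds ratios from the pooled set.

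**Working it through.** **Timing.** Entry at 2 to 4 months plus a 6-month control period gives 8 to 10 months after surgery at crossover. The two ranges do not overlap.

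**What each possible baseline and outcome visit implies for crossover patients**

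- *Study baseline to study month 3 (the literal rule).* They are still in usual care, so this change is not a response to exercise.
- *Study baseline to 3 months after crossover.* This is about 9 months of change, against 3 for everyone else, and six of those months precede exercise.
- *Month 6 to 3 months after crossover.* This is the sensible reading, but neither the Design Overview nor Table 1 schedules the second visit.

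**How many patients.** Inputs: "96 in each exercise arm and 48 in the usual care group"; for completers, "a sample size of 172 (n=86 in each exercise group"; and from the missing-data section, "we estimate the attrition to be 10% at the 3 months follow-up" and "We also estimate the attrition to be 15% at 6 months".

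- Reaching month 6: 48 × 0.85 = 40.8. With no further loss, the total is 172 + 40.8 = 212.8 and the share 40.8/212.8 = 19%.
- With a further 10% loss during the exercise phase (assumed; the plan gives no figure): 40.8 × 0.90 = 36.7, total 208.7, share 18%.
- If the total is exactly 200: 200 − 172 = 28, share 14%.

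**The plan's detectable odds ratio.** Two-proportion normal approximation, with n = N/2 per predictor level (50% split), two-sided alpha 0.05 (stated for the primary endpoint, assumed for Aim 2) and p̄ the mean of p1 and p2:

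power = Φ{ [ |p1 − p2| − 1.96·√(2p̄(1 − p̄)/n) ] / √([p1(1 − p1) + p2(1 − p2)]/n) }

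This is solved for 80% power, with OR = [p2/(1 − p2)] / [p1/(1 − p1)]. The plan does not say whether its 50% to 60% response rate is the overall rate or the rate in the reference category, so both are shown.

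| N | Convention | 50% response | 60% response |
|---|---|---|---|
| 200 | overall rate | 2.22 | 2.26 |
| 200 | reference rate | 2.26 | 2.39 |
| 172 | overall rate | 2.37 | 2.42 |
| 172 | reference rate | 2.42 | 2.58 |

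The N = 200 rows reproduce the stated 2.2 to 2.4. The N = 172 rows show Aim 2 without crossover patients.

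**Predictor count.** The Sample Size rule, min(responders, non-responders)/(predictors + 1) ≥ 10, gives floor(min/10) − 1 predictors.

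- N = 200: 100/10 − 1 = 9 at 50% response, as stated; 80/10 − 1 = 7 at 60%.
- N = 172: min = 86 gives 7 at 50%; min = 68.8 gives 5 at 60%.
- A cohort term at N = 200 leaves 8 of 9, or 6 of 7, for other predictors.

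**The case against.** The Design Overview ties assessments to before and after the intervention, and month 6 is a full visit just before crossover. A sensible analyst would probably use it as baseline. Baseline physical function is a listed predictor, and Hypothesis 2 allows adjustment for variables judged clinically important in advance. Variation in time since surgery may even be informative. Aim 2 is a predictor analysis and does not touch the 3-month treatment comparison.

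Much of this stands, and it limits the severity. It does not supply the missing outcome visit, on which the total of about 200 depends. The variables for advance adjustment are not named, so that provision is only partial cover. Informative variation in timing can be used only if the model contains it.

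A reader might go further and infer that the 20% rule misclassifies crossover patients, because the 9-point entry minimum is not re-applied and recovered patients could have very low scores. The documents do not support that:

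- They give no month-6 WOMAC-PF distribution, so no crossover patient is shown to be below 9.
- Small thresholds are not special to this group. A patient entering an original arm at 9 needs 0.20 × 9 = 1.8 points (2 whole points); at scores of 1 to 5 the requirement is 1 whole point.
- At 0 the percentage is undefined, so any error need not run in one direction.
- Response also requires 20% on the performance composite. That limits false responders, though the protection is imperfect because the composite is built from z scores, for which percentage change is unstable near zero.

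**Conclusion.** The concern holds as a gap in specification with a credible route to bias. The plan pools about 28 to 41 crossover patients, 14% to 19% of Aim 2, who start exercise six months later than the rest, with no stated baseline visit, no scheduled outcome visit and no model term. The range rests on the plan's own attrition figures and on the assumed loss after month 6; the lower end comes from reading the total as exactly 200.

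Neither the direction nor the size of the bias can be computed from the documents. It should be reported as a risk of unknown size, not as demonstrated misclassification. Aim 1 and the primary endpoint are unaffected. The change is worth making because it is cheap and removes a choice that would otherwise be made after seeing the data.

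**What to change.** Write the following into the analysis plan before Aim 2 is run:

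1. For crossover patients, define the Aim 2 baseline as the month-6 visit and the outcome as an assessment 3 months after exercise starts. Add that assessment to Table 1.
2. Include a wait-list indicator, or time since surgery, in both the univariate and the multivariable models. Because the timing ranges do not overlap, the two carry nearly the same information and one is enough.
3. Report Aim 2 also in the originally randomized exercise patients alone. A cohort term shifts the response level but does not let predictor effects differ between cohorts; this run shows whether the findings depend on pooling.
4. Treat restriction to WOMAC-PF of at least 9 at month 6 as an optional sensitivity analysis at most. It selects on a value measured after randomization and removes recovered patients.

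**Cost.** One predictor slot and one extra run. The post-crossover visit is already implied by the stated total. Function, psychosocial and impairment measures are already taken at month 6; Table 1 records medication, comorbidities and biomedical data only at study entry, so those values would be six months old unless repeated. The run at N = 172 is less sensitive: detectable odds ratio 2.37 to 2.42 (overall rate) or 2.42 to 2.58 (reference rate), with room for 7 predictors at 50% response or 5 at 60%.

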The primary outcome of this aim is the WOMAC-PF at 3 months.⁹¹ This analysis will use an intention-to-treat approach. We will analyze this aim using contrasts from a linear mixed models analysis for 3 and 6 month function controlling for baseline function and the randomization covariates (age, gender, BMI, physical function, ROM). We will first explore the intervention by time interaction, and then proceed to a main effects model with only group and time. Our primary interest is the 3 month comparison between the clinic-based individual outpatient exercise and the community-based exercise groups. The linear mixed models allow us to maximize the number of individuals used for the analyses as a person can contribute information at both time points, or just one time point. This analysis is advantageous to conducting a simple baseline adjusted ANCOVA at 3 months because persons missing 3 month data would not be included. The linear mixed model “borrows” information pertaining to the relationship between the 3 and 6 month outcomes such that persons missing either (but not both) can still be used in the analyses. To test if the improvements in outcomes are sustained, we will use contrasts from the linear mixed model at 6 months. For missing 3 and 6 month outcomes see missing data section.

For the battery of performance-based tests we will perform the analyses as described above, one for each measure. For these secondary outcomes we will use Hochberg’s step-up procedure to control the experiment-wise Type I error rate ($\alpha=0.05$),⁹² which otherwise would be inflated due to the multiple endpoints. Hochberg’s procedure is more powerful than Bonferroni adjustment and performs well when the number of endpoints is small and correlated with small to mid-size correlations. For this outcome we will also perform analysis using a composite score formed with unit-weighted z scores of constituent tests to provide a more stable measure of the subjects’ underlying functional performance.⁹³

Hypothesis 1.2- Subjects in Groups 1 and 2 will demonstrate increased physical activity as compared to Group 3.

Adjusted analysis for the outcome of physical activity will parallel the analyses described above for performance-based physical function. The outcomes of this hypothesis are real-time physical activity data captured by the SWM and self-reported physical activity from the CHAMPS questionnaire

PRINCIPAL INVESTIGATOR (LAST, FIRST, MIDDLE): [name]

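### The claim of 80% power for 5.2 WOMAC-PF points against usual care does not follow from the plan's stated inputs, which give about 95% at 5.2 points and 80% at about 4.1

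*Combined protocol and SAP*

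**What the plan says.** The Sample Size section bases its calculations on WOMAC-PF at 3 months. It randomises 96, 96 and 48 patients, assumes 10% attrition, and so expects "approximately 86 subjects in each exercise arm and 43 in the usual care group available for a complete case analysis at 3 months".

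Two power statements follow.

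- **Exercise versus exercise.** "with an alpha level of 0.05, 2 tails test", and an "SD of 7.7 from our pilot work", are said to give "81% power to detect a difference as small as 3.3-point difference between the two exercise groups in WOMAC-PF".
- **Usual care versus exercise.** "The sample size of 43 in the usual medical care group will provide 80% power to detect a difference of 5.2-point difference in WOMAC-PF", for usual care against either exercise group. This sentence gives no SD, alpha or comparator size of its own.

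Under Data Analysis, Hypothesis 1.1 reads: "Subjects in Groups 1 and 2 will demonstrate better physical function as compared to Group 3". The text below it also says: "Our primary interest is the 3 month comparison between the clinic-based individual outpatient exercise and the community-based exercise groups". Hochberg's procedure is specified there for the secondary performance tests. No division of alpha is described for the WOMAC-PF contrasts.

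**The concern.** Going from 86 versus 86 to 86 versus 43 should raise the detectable difference only moderately, yet the plan goes from 3.3 to 5.2 points at nearly the same power. That is more than the loss of patients in one arm can explain.

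The usual-care sentence is the only WOMAC-PF power statement for the exercise-versus-usual-care hypothesis, and it supports the smaller usual-care arm. If it is simply wrong, the trial's sensitivity is understated, and a null result against usual care would be read against the wrong threshold. If it rests on an undisclosed input, what follows depends on which one. A different alpha would belong in the analysis plan as well. A larger common SD would apply equally to the comparison of primary interest.

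**Working it through.** **Inputs, all from Sample Size.** Two-sided alpha 0.05; SD 7.7; 3-month completers 86, 86 and 43 (96 × 0.9 = 86.4; 48 × 0.9 = 43.2). Alpha and SD are carried over from the exercise-versus-exercise sentence to the one that follows it. No other WOMAC-PF SD appears in the document.

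**Method.** Two-sample t-test with noncentral-t power: SE = SD × √(1/n₁ + 1/n₂), noncentrality = difference / SE, degrees of freedom n₁ + n₂ − 2.

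**Step 1: the plan's exercise-versus-exercise figure.** SE = 7.7 × √(2/86) = 1.174. Noncentrality = 3.3 / 1.174 = 2.81. Power is 79.8% (80.2% by the normal approximation), against 81% stated. This is close enough to show that the inputs are read as intended.

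**Step 2: the usual-care figure.** SE = 7.7 × √(1/43 + 1/86) = 1.438. Noncentrality = 5.2 / 1.438 = 3.62. Power is **94.8%** (95.1% by the normal approximation), not 80%. The difference detectable with 80% power is **4.06** points (normal approximation: (1.960 + 0.842) × 1.438 = 4.03). The stated figure is larger by 5.2 / 4.06 = 1.28, that is 28%.

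**Step 3: a check that does not depend on the SD.** With one common SD, one alpha and equal power, the two detectable differences should stand in the ratio √(1/43 + 1/86) / √(2/86) = √1.5 = 1.22. The plan's figures give 5.2 / 3.3 = 1.58. The step from 81% to 80% power is far too small to explain this, so no single SD and alpha yields both sentences at these sample sizes.

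**Step 4: which changes would give 5.2?**

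| 86 v 43 unless stated, SD 7.7 | Power at 5.2 | 80% detectable difference |
|---|---|---|
| alpha 0.05 (as stated) | 94.8% | 4.06 |
| alpha 0.025 | 91.0% | 4.48 |
| alpha 0.0167 | 88.1% | 4.71 |
| 43 v 43, alpha 0.05 | 87.2% | 4.71 |
| 43 v 43, alpha 0.025 | 80.0% | 5.20 |
| 48 v 48, alpha 0.0167 | 80.6% | 5.17 |

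Changing one input alone, 80% power at 5.2 points needs one of these:

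- alpha of about 0.0065;
- a common SD of about 9.9;
- about 31 patients in the exercise arm;
- an SD of about 10.7 in usual care only, keeping 7.7 in the exercise arm (Welch test).

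The plan states none of these.

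**Step 5: sensitivity to the SD, 86 v 43, alpha 0.05.**

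| Common SD | 80% detectable difference | Power at 5.2 |
|---|---|---|
| 7.0 | 3.69 | 97.7% |
| 8.5 | 4.48 | 90.2% |
| 9.5 | 5.01 | 82.9% |

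**Step 6: the consequence if a common SD of 9.86 was used.** The 3.3-point exercise-versus-exercise comparison would then have 58.8% power, and its 80% detectable difference would be 4.24 points.

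**The case against.** The strongest reply is that the usual-care sentence does not say it uses SD 7.7 or alpha 0.05, so carrying them over is an assumption. A coherent derivation also exists: equal groups of 43 with alpha halved for two comparisons against usual care gives 80.0% power at 5.20 points. On that view the figure is a conservative calculation with its assumptions left out. The reply adds that the 59% scenario is hypothetical: a different alpha, a different comparator size, or a larger SD in usual care alone would leave the 3.3-point comparison untouched. Finally, the error is conservative, and the comparison of primary interest reproduces.

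Much of this stands. How 5.2 arose cannot be settled from the document, the 59% figure is conditional, and the sample size is not shown to be inadequate. But the reconstruction needs two assumptions the plan does not state, and 43 versus 43 contradicts its own 86 per exercise arm. If alpha was halved for these contrasts, the analysis section should say so, and it does not. The sentence remains irreproducible from what the plan provides.

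**Conclusion.** The concern holds. With SD 7.7, two-sided alpha 0.05 and 86 versus 43 completers, power at 5.2 points is 94.8% and 80% power is reached at 4.06 points. The plan states 80% at 5.2.

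The conclusion assumes that alpha and SD carry over from the preceding sentence. The ratio check needs less: a common SD and the same alpha in both sentences, whatever their values. Either an input is unstated or the figure is wrong.

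The practical effect is modest. On the stated inputs the design is more sensitive than claimed, and neither sample size nor allocation needs to change. It should still be corrected, because this is the power statement for Hypothesis 1.1 on the primary endpoint, and because only the sponsor can exclude a larger common SD that would weaken the exercise-versus-exercise comparison.

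**What to change.** Establish which SD, alpha and comparator size were used for the usual-care calculation.

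- **If they are those already in the section**, replace the sentence with: With 86 in an exercise arm and 43 in usual care, SD 7.7 and two-sided alpha 0.05, power is 80% for a 4.1-point and 95% for a 5.2-point difference in WOMAC-PF.
- **If alpha was adjusted**, state the adjustment here and under Hypothesis 1.1, and recompute at 86 versus 43: 4.5 points at alpha 0.025, 4.7 at alpha 0.0167.
- **If the SD differs**, give it, say whether it applies to all arms, and if so recompute the 3.3-point statement too.

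At the same time, give the SDs and exact power behind the secondary detectable differences. Their usual-care to exercise-versus-exercise ratios run from 1.6/1.4 = 1.14 to 0.03/0.02 = 1.50. With rounded values, no SDs and power given only as above 80%, they are not shown to be wrong.

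The cost is a text correction. Sample size, allocation and analysis are unchanged, unless the sponsor finds that alpha was in fact adjusted or a larger common SD applies.
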